### 11.4.3 ECG

A single 12-lead resting digital ECG will be recorded after the subject has been supine for at least 5 minutes at the visits indicated in the schedule of trial procedures (Section 4).

A pre-evaluation of the ECGs will be performed by the investigators to evaluate immediate subject safety. At a minimum, date of ECG collection will be recorded in the source documents.

The ECG data will be transferred to a central ECG service company for central evaluation. A cardiologist at the ECG service company will analyse and interpret the ECG data. The ECG service company will provide ECG evaluation reports to the trial sites.

The investigator must evaluate all abnormal ECG results ('clinically significant' or 'not clinically significant') and sign and date. The investigator has the final decision on the clinical

significance of ECG abnormalities. If a result is abnormal at the screening visit and considered by the investigator to be clinically significant, it will be up to the investigator's discretion if the subject should be enrolled into the trial (respecting exclusion criterion no. 27); if such a subject is enrolled, the investigator will provide a justification in the medical record.

The collection and transmission of ECG data will be described in a separate ECG manual. Test dummy transmissions will be undertaken prior to trial conduct to ensure that transmissions can be made and that date and time settings are correctly set.

### **Reporting in eCRF**

It will be recorded in the eCRF if an ECG was performed and, if applicable, the investigator's assessment of ECG results ('normal', 'abnormal, not clinically significant', 'abnormal, clinically significant'). If an ECG was not performed, a reason should be given.

Clinically significant abnormal ECG findings at the (first) screening visit will be documented as medical history in the eCRF. If an abnormal ECG at any other visit than the first screening visit is considered by the investigator to be clinically significant, it will be reported as an AE in accordance with Section 13.3. Further, any clinically significant deterioration of a pre-existing condition as well as any new clinically significant sign, symptom or illness observed after screening will be reported as an AE in accordance with Section 13.3.

### **11.4.4 Pregnancy test**

A serum pregnancy test must be taken at the screening visit in female subjects of child-bearing potential as described in the schedule of trial procedures in Section 4.

A urine pregnancy test (human chorionic gonadotropin; dipstick) must be performed at the trial site at baseline prior to randomisation in female subjects of child-bearing potential. The test must be repeated every 4 weeks as shown in the schedule of trial procedures in Section 4. The visit date and the outcome of the urine pregnancy test will be recorded in the eCRF ('positive', 'negative').

Note that pregnant subjects must discontinue IMP immediately (Section 10.2.1).

### 11.4.5 Laboratory testing

Samples for laboratory testing will be collected according to the schedule of trial procedures (Section 4).

The following safety samples will be analysed by a central laboratory: chemistry, haematology, serology, and serum pregnancy ([Panel 11](#)).

Urine samples will be tested at the trial site with a dipstick; if abnormal, a urine sample will be sent to the central laboratory for further analysis.

A laboratory manual will be provided to the sites that specifies the procedures for collection, processing, storage, destruction, and shipment of samples, as well as laboratory contact information specific to this trial.

**Panel 11: Clinical laboratory tests**

Chemistry	Haematology
Sodium	Erythrocytes
Potassium	Hematocrit
Creatinine	Hemoglobin
Urea nitrogen	Erythrocyte mean corpuscular volume
Calcium	Erythrocyte mean corpuscular haemoglobin concentration
Alkaline phosphatase	Leukocytes
Aspartate aminotransferase	Neutrophils
Alanine aminotransferase	Neutrophils/leukocytes
Gamma glutamyl transferase	Lymphocytes
Bilirubin 	Lymphocytes/leukocytes
Lactate dehydrogenase	Monocytes
Cholesterol	Monocytes/leukocytes
LDL cholesterol	Eosinophils
HDL cholesterol	Eosinophils/leukocytes
Triglycerides	Basophils
Glucose (non-fasting)	Basophils/leukocytes
Albumin	Thrombocytes
Protein	
Tryptase 	
	Serology
	Hepatitis B virus surface antigen 
	Hepatitis B virus surface antibody 
	Hepatitis B virus core antibody 
	Hepatitis C virus antibody 
	HIV-1 antibody 
	HIV-2 antibody 
	Immunoglobulin E 
Urinalysis 	Serum pregnancy test 
Protein	Choriogonadotropin beta
Glucose	
Ketones	
Occult blood	
Leukocytes	
Nitrite	

- 1) If bilirubin is above upper limit of normal, direct and indirect bilirubin will also be measured.
- 2) Only measured in case of suspected anaphylaxis (Section 9.2.1).
- 3) Urine samples will be tested at the trial site (dipstick). In case of abnormal dipstick results, a urine sample will be sent to the central laboratory for microscopic examination (leukocytes, erythrocytes, and casts).
- 4) Measured at screening only.
- 5) Not measured at screening.
- 6) Only female subjects of child-bearing potential.

HDL, high density lipoprotein; HIV, human immunodeficiency virus; LDL, low density lipoprotein.

The investigator must evaluate all results outside the reference range ('clinically significant' or 'not clinically significant') and sign and date. The signed and dated version will be filed with the investigator's trial documentation. Clinically significant abnormal tests at baseline (Week 0) or later must be repeated to confirm the abnormality.

If a screening laboratory result is abnormal and of clinical significance, it will be at the investigator's discretion to decide if the subject should be enrolled into the trial (respecting exclusion criteria no. [27](#), [28](#), and [29](#)).

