**Panel 2: Schedule of trial procedures (continued)**

Visit	Screening		Treatment period									Follow-up 			Uns. visit  (if appl.)	Early term.  (if appl.)	Nominal Week 16 visit  (if appl.)	References (protocol section)
	1 	2	3	4	5	6	7	8	9	10	11 	12 	13 	14 			11x	
Week	-6	-2	0	2	4	6	8	10	12	14	16	20	24	30			16	
Visit window (days) 	±3	-3	NA	±3	±3	±3	±3	±3	±3	±3	±3	±3	±3	±3	NA	NA	±3	
Investigator assessments of safety																		
Vital signs	X		X 	X 	X 	X	X	X	X	X	X			X	X 	X		11.4.1
Physical examination	X		X				X				X			X	X 	X		11.4.2
ECG	X		X								X			X	X 	X		11.4.3
Chemistry, haematology, IgE (central laboratory)	X 		X		X		X		X		X			X	X 	X		11.4.5
Serum pregnancy test; hepatitis B, C; HIV (central laboratory)	X																	11.4.4; 11.4.5
Urine pregnancy test			X		X		X		X		X			X	X 	X		11.4.4
Urinalysis	X		X		X		X		X		X			X	X 	X		11.4.5
Anti-drug antibodies			X		X						X			X	X 	X		11.4.6
Pharmacokinetics					X						X			X	X 	X		11.6
Adverse events	X	X	X	X	X	X	X	X	X	X	X	X	X	X	X 	X	X	13
Assessment of vaccine antibody response																		
Anti-tetanus response									X		X				X 	X 	X 	11.5
Anti-meningococcal response									X		X				X 	X 	X 	11.5

- 1) For subjects who do not require a wash-out, visits 1 and 2 will be combined and screening will be reduced to 2 weeks; hence, these subjects will only attend visit 2 (Week -2) which will include all assessments shown under Week -6. Similarly, for subjects who only require a 2-week wash-out, screening visits 1 and 2 will be combined (Week -2). The screening period has a maximum duration of 6 weeks.
- 2) Eligible subjects may roll over to the ECZTEND trial at Week 16 or later. See also footnote no. 5.
- 3) All subjects, except for those who roll over to the ECZTEND trial (LP0162-1337), will have a full 14-week off-treatment safety follow-up period. The safety follow-up period includes 2 telephone contacts and an office visit (end-of-trial visit) at Week 30. Subjects may transfer to the ECZTEND trial at any time during the safety follow-up period.
- 4) Visit will be conducted as a telephone contact.

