- 5) An end-of-treatment form and end-of-trial form must be completed in the eCRF for all randomised subjects. See Section 11.10 for further details.
- 6) Assessments and procedures to be performed at an unscheduled visit are left at the investigator's discretion.
- 7) Subjects who permanently discontinue IMP or withdraw from the trial will be followed up as described in Section 10.3 and will have a final safety follow-up visit 16 weeks after last dose of IMP.
- 8) Subjects who permanently discontinue IMP prior to Week 16 will also attend the nominal Week 16 visit (visit 11x).
- 9) If the date of a trial visit does not conform to the clinical trial protocol, subsequent visits should be planned to maintain the visit schedule relative to baseline.
- 10) The informed consent form must be signed prior to performing any protocol-related procedures, including but not limited to screening evaluations and wash-out of disallowed medications.
- 11) All subjects must use an emollient twice daily (or more, as needed) for at least 14 days before randomisation and must continue this treatment throughout the trial (including safety follow-up).
- 12) For the first 3 IMP (tralokinumab/placebo) dosing visits, subjects will be monitored after IMP administration for immediate drug reactions for a minimum of 30 minutes with vital signs taken at 30 minutes or until stable, whichever is later (Section 9.2.1).
- 13) Since the 2 vaccinations will be given in the upper arms (1 vaccine in each arm), the IMP (tralokinumab/placebo) injections at Week 12 will be given at a different anatomical site (that is, anterior thigh or abdomen).
- 14) Where it is not allowed to collect the subject's full date of birth per local legislation, the subject's age in years will also be recorded.
- 15) The total body surface area affected by AD will be assessed by the investigator as component A of SCORAD.
- 16) IgE not measured at screening.
- 17) Only to be considered if the unscheduled visit occurs after Week 12 (that is, after administration of the vaccines).
- 18) Only required if the subject permanently discontinues IMP (tralokinumab/placebo) after Week 12 (that is, after administration of the vaccines).

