## 5 Introduction and trial rationale

### 5.1 Atopic dermatitis

AD is a chronic inflammatory skin disease that may affect up to 20% of children and up to 10% of adults. In its severe form, AD is characterised by widespread skin lesions, intractable itch, as well as enhanced susceptibility to bacterial, viral, and fungal skin infections (1-4). AD is associated with a substantial patient burden that typically includes poor quality of life, sleep disturbance, and reductions in work productivity (5).

AD is characterised by an activated Th2 pathway with increased skin expression of key Th2 cytokines including IL-13 (6, 7). The expression of IL-13 is increased in lesional skin compared to non-lesional skin, and the proportion of CD4+ and CD8+ cells expressing IL-13 is upregulated in AD patients compared to individuals without AD (6, 8).

IL-13 acts on keratinocytes to release CCL22 and recruit more IL-13 expressing Th2 cells, decrease differentiation, and contribute to decreased barrier function (9). IL-13 also drives IgE production and contributes to mast cell activation status and, once allergen cross-links IgE on the cell surface, drives histamine release and induces itch (10, 11). Indeed, itch is a key issue in AD, which drives significant mechanical damage to the skin and further facilitates allergen and pathogen entry.

All of these effects together drive and exacerbate the disease phenotype. A review of the available preclinical literature from mouse and human ex-vivo models suggests IL-13 as a, if not the, central mediator of the AD skin phenotype. Indeed, there is evidence that blocking the IL-4 receptor (which is part of the receptor complex which also binds IL-13) with the monoclonal antibody dupilumab leads to clinical improvement in AD subjects (12).

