### 5.2 Experience with investigational medicinal product

Tralokinumab is a human recombinant monoclonal antibody of the IgG4 subclass that specifically binds to human IL-13 and blocks interaction with the IL-13 receptors (13-15). A compilation of clinical and nonclinical data on tralokinumab including PK is given in the current version of the Investigator's Brochure.

In total, 14 clinical trials have been conducted with tralokinumab, with phase 3 development ongoing in AD. Other clinical trials with tralokinumab have been conducted in subjects with asthma, ulcerative colitis, idiopathic pulmonary fibrosis, and in healthy subjects. Further information on these trials can be found in the current version of the Investigator's Brochure.

In a phase 2b trial (D2213C00001), adults with moderate-to-severe AD on a background of mild to moderate TCS, were treated with 3 different regimens of tralokinumab (45 mg Q2W, 150 mg Q2W, or 300 mg Q2W) or placebo to evaluate the safety and efficacy over a treatment period of 12 weeks. The primary endpoints were change from baseline in EASI at Week 12 and the percentage of subjects achieving IGA response of 0 (clear) or 1 (almost clear) at Week 12. Secondary endpoints included change from baseline in EASI and SCORAD scores, EASI50, and SCORAD50. In the overall intent-to-treat phase 2b population, an improvement in EASI score at Week 12 was seen in the tralokinumab 300 mg Q2W group versus placebo. 26% of subjects achieved an IGA of 0 or 1 in the tralokinumab 300 mg Q2W group versus 12% in the placebo group. The most commonly reported causally related treatment emergent adverse event was upper respiratory tract infection (6 [3.9%] subjects in the combined tralokinumab group (45 mg, 150 mg, and 300 mg) and 2 [3.9%] subjects in the placebo group).

In total, more than 2,343 subjects have been treated with tralokinumab (cut off date: 18-Aug-2017). The safety of all doses studied so far has been with an acceptable benefit-risk profile and no major safety concerns have been identified. Possible risks associated with use of tralokinumab are summarised in Section 5.5.

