### 9.3.1 Blinding

This is a double-blinded trial in which tralokinumab and placebo are visually distinct from each other. Neither the subject nor any of the investigator or LEO staff who are involved in the treatment or clinical evaluation and monitoring of the subjects will be aware of the treatment received. The packaging and labelling of the IMPs will contain no evidence of their identity.

Since tralokinumab and placebo are visually distinct and not matched for viscosity, IMP (tralokinumab/placebo) will be handled and administered by a qualified, unblinded HCP at the site who will not be involved in the management of trial subjects and who will not perform any of the assessments.

In the event that the treatment allocation for a subject becomes known to the investigator or other study staff involved in the management of trial subjects, LEO must be notified immediately.

Should an issue arise with the IMP (e.g., damaged kit or syringe that has been assigned to a subject prior to administration, or any other unexpected event with the kit or syringe [e.g., a malfunction during IMP administration]), the unblinded HCP at the site will contact the CRA to determine whether any specific actions are required.

The trial site will maintain a written plan detailing which staff members are blinded/unblinded and the process of IMP administration used to maintain the blind.

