### **Reporting in eCRF**

At each visit, the site staff will record the following in the eCRF: Date and time of blood sample (or that a blood sample was not taken) and the investigator's assessment of the results ('normal', 'abnormal, not clinically significant', 'abnormal, clinically significant'). In addition, the site staff will record in the eCRF if a urine sample was taken and the investigator's assessment of the result ('normal', 'abnormal').

Clinically significant abnormal laboratory findings at the (first) screening visit will be documented as medical history in the eCRF. If an abnormal laboratory finding at any other visit than the first screening visit is considered by the investigator to be clinically significant, it will be reported as an AE in accordance with Section [13.3](#). Further, any clinically significant deterioration of a pre-existing condition as well as any new clinically significant sign, symptom or illness observed after screening will be reported as an AE in accordance with Section [13.3](#).

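### Post-baseline IgE is not exempt from investigator review, so the IGA and EASI rater may see a possible hint of allocation before the Week 16 rating

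*Protocol*

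**What the plan says.** **Sampling.** In Panel 2 of the protocol, the row that begins "Chemistry, haematology, IgE (central laboratory" has samples at Weeks 0, 4, 8, 12, 16 and 30, and at unscheduled and early termination visits where these apply. A footnote adds "IgE not measured at screening", so the first value is the Week 0 one.

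**Review.** Panel 11 lists IgE under serology. The text below the panel reads "The investigator must evaluate all results outside the reference range", followed by a duty to classify, sign, date and file the results. Clinically significant abnormal tests from baseline onwards must be repeated. The eCRF paragraph of Section 11.4.5 has the site record, at each visit, "the investigator's assessment of the results ('normal', 'abnormal, not clinically significant', 'abnormal, clinically significant". No test is exempt.

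**Mechanism.** Section 5.1 says "IL-13 also drives IgE production and contributes to mast cell activation status". Section 5.2 says that tralokinumab "specifically binds to human IL-13 and blocks interaction with the IL-13 receptors".

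**Blinding.** Section 9.3.1 promises that "Neither the subject nor any of the investigator or LEO staff who are involved in the treatment or clinical evaluation" will know which treatment was given. The measures it describes deal with the look and viscosity of the syringes and with an unblinded person who gives the injections. Laboratory results are not mentioned. Section 11.1 keeps assessors away from IMP administration only, and asks for one investigator to do all of a subject's evaluations where possible. The SAP adds no masking of IgE.

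**The concern.** IGA 0/1 and EASI75 at Week 16 are the two secondary efficacy endpoints. Both are scored by the investigator and both are in the hierarchical testing procedure for superiority. A rater who suspects the allocation may score differently at the boundary between almost clear and mild. Rescue treatment is at the investigator's discretion and turns a subject into a non-responder in the primary analysis of these endpoints, so suspicion could also act through that decision.

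IgE is a laboratory value that the protocol itself links to the drug's target. If it fell under tralokinumab and not under placebo, a rater who followed the series would have information about allocation from outside the skin being rated. The protocol takes care to close the syringe route and leaves this one unaddressed.

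**Working it through.** The check is mainly a comparison of passages.

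1. **Can the result reach the rater?** IgE is in Panel 11, and the investigator must evaluate and sign whatever is out of range. Appendix 4 lists raised serum IgE as a minor diagnostic feature of AD, so out-of-range values are to be expected; the share of subjects is not given. The eCRF assessment includes a category for normal results, so review is not confined to abnormal values. Nothing separates the laboratory reviewer from the IGA and EASI rater. Delivery of IgE to the site is thus implied by the sign-off duty, but is not stated.

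2. **Which values matter?** Week 0 is the reference. The Week 16 sample is drawn at the rating visit and Week 30 comes after it. That leaves Weeks 4, 8 and 12, read against Week 0, plus any unscheduled sample. The Week 12 value has about four weeks to be reported.

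3. **Which direction?** IL-13 promotes IgE, and the drug blocks IL-13. A fall in IgE is a reasonable inference from these two statements. No size, speed or between-subject spread is given.

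4. **How are comparable results handled?** Under Section 11.5, vaccine antibody reports go to sites at the end of the trial. For ADA and PK (Sections 11.4.6 and 11.6), the eCRF records whether the sample was taken, and no investigator review is asked for. IgE has no such protection.

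5. **Does any rule need IgE at the site?** It is in none of the eligibility criteria (Sections 8.2 and 8.3), none of the discontinuation reasons (Section 10.2), and not in the SAP's Table 4 of potentially clinically significant values.

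6. **Which endpoints are exposed?** IGA 0/1, EASI75 and the other endpoints built on EASI and the investigator-scored parts of SCORAD. The two vaccine responses are immunoassay results.

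**The plan's own figures.** Section 14.1 gives 98% power for tetanus non-inferiority and about 89% for all four hypotheses. With 80 per arm, 80% response in both arms and a margin of 25 points: Φ(0.25/√(2×0.8×0.2/80) − 1.96) = Φ(3.95 − 1.96) = 97.7%. With 100 per arm, a pooled-variance test gives 94.8% for IGA 0/1 (30% v 10%) and 98.1% for EASI75 (40% v 15%). The product is 0.977 × 0.977 × 0.948 × 0.981 = 88.8%. Both figures reproduce, and this point changes neither.

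**Illustration only.** The documents give no figure for scoring bias, so the sizes below are assumptions and not estimates. Suppose that there is no true effect, that each arm has 100 subjects, and that biased scoring lifts the tralokinumab response rate by b points. Let X ~ Bin(100, p+b) and Y ~ Bin(100, p), and reject if (X−Y)/100 ÷ √(2m(1−m)/100) > 1.96, where m = (X+Y)/200. Exact enumeration, ignoring strata and taking each test on its own, gives these one-sided rejection rates:

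| Assumed lift b | p = 10% (IGA 0/1) | p = 15% (EASI75) |
|---|---|---|
| 0 | 2.6% | 2.5% |
| 2 points | 6.7% | 5.9% |
| 5 points | 18.8% | 15.4% |
| 10 points | 51.8% | 43.0% |

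The table shows that these tests are sensitive to small rating shifts. It does not show that IgE would cause one.

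**The case against.** The strongest reply is that nothing shows IgE would reveal the arm. To unmask, it would have to separate the arms subject by subject within 12 weeks, and the documents are silent on that. The required task is only to mark out-of-range values as clinically significant or not. A raised IgE that stays raised would be marked in the same way in either arm, so only a rater who tracks the numbers would learn anything. Section 11.7 declares pharmacodynamics not applicable, so the protocol does not treat IgE as a drug marker. A separate laboratory manual exists and could already mask it. Raters also see the skin every two weeks, and with planned IGA response of 30% v 10% that is a hint in itself.

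Most of this stands as a limit on size. It does not close the route. The manual's contents as listed in Section 11.4.5 are sample procedures and contact details, with no mention of masking. Visible improvement is the outcome being rated, whereas IgE is outside information that can be withheld without loss to the assessment.

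A reader might infer that Section 9.3.1 is contradicted. It is not: seeing a non-specific laboratory value is not the same as knowing the treatment.

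**Conclusion.** The point holds as a possible and unquantified leak. As written, the IGA and EASI rater may see IgE from baseline and Weeks 4, 8 and 12 before the Week 16 rating, and on the protocol's own account of the mechanism a fall could hint at allocation. It affects only the investigator-rated secondary and other efficacy endpoints.

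This rests on three assumptions: that site laboratory reports include IgE, that the reviewer and the rater are the same person or share results, and that IgE moves enough under tralokinumab to be noticed.

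Stronger readings are tempting and are not supported. The documents do not show that raters will be unblinded, do not say that tralokinumab lowers circulating IgE, and give no basis for stating how many points the treatment difference would be inflated by. The primary vaccine conclusions are not put in doubt. The point ranks as a cheap improvement.

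**What to change.** In Sections 9.3.1 and 11.4.5, state that post-baseline IgE results are withheld from sites and from blinded sponsor staff until unblinding, as is already done at sites for vaccine antibody reports. In Section 11.4.5, exempt post-baseline IgE from investigator evaluation, sign-off, repeat testing and the per-visit eCRF assessment; without these exemptions the new sentence would conflict with existing duties. If the laboratory manual already masks IgE, the protocol should say so.

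The cost is a change to the central laboratory's report configuration and a few lines of protocol text. IgE is still measured and summarised, and all other safety results are reported as now. The change helps only for results not yet sent, so it should be in place before the first Week 4 results are reported. The downside is that sites cannot see IgE during the trial. IgE is scheduled under safety assessments, so the sponsor should confirm that this is acceptable, but no eligibility, discontinuation or potentially-clinically-significant rule uses it.
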